This proposed intervention will not directly deprescribe medications; we will not be randomizing patients to medication discontinuation. Instead, we are testing an intervention to prompt consideration of a clinical decision, analogous to a clinical reminder in the electronic health record prompting the provider to consider appropriate care. We propose an innovative approach to promote medication use review that starts by contacting the patient, not the clinician, yet the ultimate decision remains with the patient-provider dyad.

Study Aim

The study primary aim is to examine the impact of a patient-centered intervention to change provider prescribing (the primary outcome), as determined by the frequency with which medications are either deprescribed or de-escalated. Our primary outcome will be the composite of deprescribing and de-escalation of target medications, identified in pharmacy dispensing records of the Corporate Data Warehouse (CDW).

Hypothesis

The hypothesis is deprescribing will be greater for Veterans receiving the intervention brochure than for those in the historical control group.

Study sites

We will target Veterans at three primary care sites who meet eligibility criteria and are prescribed the target medication at the time of their scheduled primary care visit (in-person, video technology-based, or telephone clinics). These sites were selected based upon ability to recruit adequate samples, geographic variability, and patient population. We will include all PCPs at VA Medical Centers (VAMCs) and Community Based Outpatient Clinics (CBOCs), except for resident clinicians, as these trainees are likely to turn over during the intervention.

Randomization

Previous research, including our pilot study, revealed differences in deprescribing tendencies across providers. Thus, although our intervention intends to engage patients, our study design prioritizes comparisons of patients within the same provider to maximize power. At each intervention site, individual PCPs will be randomized to the sequence of medication cohorts. We will randomize PCPs to one of the three medication groups at the beginning of the first (month 1) and second (month 7) window and assigned them to their

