remaining medication group at the start of the third (month 13) window. Our primary comparisons are between “brochure-intervention” patients and “baseline” patients (matched in terms of eligibility) from the same provider. Each patient will only have one opportunity to receive a brochure, even if they subsequently meet eligibility criteria for receipt of a second, different brochure. This allows equal exposure to the intervention for all Veterans since the impact of a second brochure might be influenced by the first brochure.

Although our primary comparison is between patients of the same provider pre- and post-intervention, we will also collect data at non-equivalent control sites matched by geography who will not receive the intervention; all data on control patients will be from the Corporate Data Warehouse (CDW). Including additional control sites will allow us to address potential temporal trends in deprescribing over the timeframe of our study that are not due to our intervention. The use of separate control sites (rather than randomizing some PCPs at each intervention site to control conditions) was preferred due to concerns about potential contamination across intervention and control conditions within sites. For both the control sites and the pre-intervention baseline period, we will identify patients who would have been eligible for the study; patients meeting criteria for multiple cohorts will be randomly allocated to only one.

Study Cohorts

The intervention cohort will consist of eligible patients in one of the three medication groups with an upcoming PCP appointment during the study enrollment period. We will create a comparison historical control cohorts comprising eligible patients in each medication group who were seen by the same PCPs at the same sites as our intervention cohort eighteen months to one year before our intervention cohort window to allow for comparable follow-up time before the intervention commenced. Patients in the intervention cohorts will be excluded from the historical control cohorts.

Medication Groups

To be enrolled in the study intervention or control cohort, patients needed to meet eligibility criteria for one of three medication-based groups. We have selected three medication-based patient groups based upon variations in 1) type of potentially inappropriate use, 2) medication factors (potential benefit and harms of continued use), and 3) anticipated interest in deprescribing by patients and providers.

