We will query CDW for 6 months following the date of each scheduled primary care visit to assess our primary outcome of deprescribing. Based upon findings in our pilot study, medication orders may not be discontinued in electronic health records even if discussions occur in the clinic visit (e.g., the PCP tells the patient to deprescribe but does not change the order). Notably, because our primary objective is to improve safe prescribing and reduce PIMs, pharmacy dispensing data best reflects our deprescribing outcome. As per our definition, either complete cessation or dose reduction will be fulfillment of our primary outcome.

Modeling our approach after the methods of Steinman, Sussman, and Martin, we will use non-refill of the medication in the 6 months following the primary care appointment as our a priori definition of cessation, based upon dispensing dates.^{4,5} Per VA Pharmacy policy, medications are only refilled upon request, and therefore, non-refill of a medication can indicate that it was discontinued, it expired (typically one year after it was ordered), or the patient did not refill it. If the medication continues to be dispensed, we will determine any reduction in the total daily dose, indicating de-escalation (one component of our deprescribing definition). An

exception to the de-escalation rule will be for insulin, where only complete cessation will qualify since dose changes are less likely to be reflected in the order compared to oral medications.

Consistent with our conceptual framework, we will also assess patient and provider factors that may influence deprescribing. Patient factors will be obtained from CDW, and will include age, race, sex, Elixhauser comorbidities in the two years prior to the scheduled primary care visit. Provider factors include sex, discipline, age, and site.

To assess potential ADWEs, we will ascertain if the deprescribed medication is subsequently restarted or returns to original dosing. We will then query CDW for diagnoses of GI bleeding for the PPI cohort, diabetic ketoacidosis or hyperosmolar hyperglycemic state for the DM cohort, and seizure for the gabapentin cohort in the year following the index visit. Note, we consider substitution to a lower potency medication (e.g., histamine-2 receptor antagonist for a PPI) to be a neutral or desirable event and not an ADWE.

Statistical Analysis Plan (see attached statistical analysis plan for greater detail)

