To identify dose reductions, we calculated the total daily dose (TDD) of the target medication as [dose*(quantity/days supplied)].^{1,2} Substitutions within a medication drug class (e.g., pantoprazole to omeprazole) were standardized to one medication within each class. We only compared TDD at 6 months to that at the index visit for oral medications because insulin dose adjustments are not consistently documented within the electronic health record. Combination insulin products were separated into their long acting and short acting components and analyzed separately. We allowed a 10% buffer for days' supply of PPI, sulfonylurea, and gabapentin (e.g., 33 days for a 30-day supply) to account for missed doses and 100% buffer for insulin due to dispensing requirements (e.g., minimum vials dispensed regardless of dose).

Patient factors and provider characteristics (age, gender, profession) were included as covariates in the model. Based on our conceptual model and using data from CDW, patient factors included age, race, sex, and Elixhauser comorbidities in the year prior to the scheduled primary care visit.^{4,5}

Additionally, we planned to examine whether the effectiveness of the brochure intervention was associated with target medication.

Interim & Final Analysis

Our primary comparisons were between “brochure-intervention” patients and “historical control” patients (matched in terms of eligibility) from the same primary care provider. To investigate the impact of the intervention brochure on deprescribing, Hierarchical Generalized Linear Modeling (HGLM) was used to account for the nesting of patients within providers. This approach provided information not just about the average effectiveness of the intervention, but also about how much variation there is in the intervention impact across providers. In all models, Level 1 (patient-level) intercepts and slopes were treated as random effects, and parameters were estimated with robust standard errors. Using this approach of nesting patients within providers at intervention sites, for our primary analysis, we compared the likelihood of deprescribing among patients in the pre-intervention (“historical”) period to that for patients in the intervention periods who were mailed the brochure. We predicted that intervention patients would be significantly more likely to have deprescribing than patients in the pre-intervention period with the same eligibility criteria. We then examined whether the

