intervention effectiveness was moderated by the target medication. We did not expect a discontinuation rate of 100%, as patients may have an indication to remain on the medication. No adjustments were made to p-values or confidence intervals for multiple comparisons for the primary outcome.

No interim analyses were planned.

Missing Data

We examined the incidence of missing data by medication cohort (PPI vs. DM vs. Gaba). We expected very low rates of missing data, given that our primary analyses rely on CDW data. For missing data, we implemented a series of sensitivity analyses using imputation (coding as “missing” for categorical variables and imputed means for continuous variables) to assess the degree of bias that might be induced by missing data. The results did not change in direction or significance.

Methods for dealing with data transformations

We did not apply any data transformations. All data underwent standard preliminary visualization and quality screening to test for potential violations of assumptions (e.g., distributional assumptions regarding normality, homogeneity of variance, linear relationships, outliers, ceiling/floor effects).

Other analytical subsets

The intervention is designed to target and engage patients, but it is possible that the intervention may be more effective with certain providers. Therefore, a null hierarchical model was used to estimate intraclass correlations to characterize the percent variance explained at the patient, provider, and site levels.

We used HGLM to examine whether the likelihood of deprescribing changes over time at our control sites (instead of from the pre-intervention period) to rule out alternative explanations for the effect of our intervention that rely on temporal trends in deprescribing unrelated to our intervention (e.g., other deprescribing initiatives). We elected not to include temporal deprescribing trends in the manuscript since there was no evidence of significant temporal trends.

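### The protocol lists site as a provider factor but the SAP's primary model omits it, so stable site differences can enter the brochure estimate if the brochure-to-historical ratio varies by site

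*SAP*

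**What the plan says.** Under Study Measures, the protocol names the factors that may influence deprescribing. For providers it says: "Provider factors include sex, discipline, age, and site".

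The SAP, under Endpoints & Covariates, says that patient factors and "provider characteristics (age, gender, profession) were included as covariates in the model". Sex, discipline and age reappear there as gender, profession and age. Site does not, and no reason is given.

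Site returns once in the SAP, under Other analytical subsets, where a null hierarchical model is used to "characterize the percent variance explained at the patient, provider, and site levels".

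The primary comparison sets brochure patients against historical controls of the same providers. The protocol states the intent under Randomization: "our study design prioritizes comparisons of patients within the same provider to maximize power". Under Study Cohorts, the historical patients are those "seen by the same PCPs at the same sites as our intervention cohort". The model is an HGLM with patients nested in providers, random intercepts and slopes, and robust standard errors.

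The same covariate lists differ on a second item. The protocol specifies "Elixhauser comorbidities in the two years prior to the scheduled primary care visit", whereas the SAP takes comorbidities from one year before the visit.

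**The concern.** The primary estimate is meant to compare patients within a provider. A random provider intercept delivers that only approximately. It pulls each provider towards the overall mean, and the pull is strong when a provider contributes only one or two events. Whatever part of a stable site difference is not captured by the intercepts remains available to any covariate correlated with site. Brochure status is such a covariate if one site supplies proportionally more brochure patients than another.

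A site with a higher underlying deprescribing rate and a larger brochure share would then inflate the brochure effect. The reverse pattern would mask a real effect. Robust standard errors do not correct a shifted coefficient, and the null model cannot adjust the brochure estimate because it contains no brochure term.

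The preconditions are not far-fetched. The protocol says the sites were chosen partly for variety in geography and patient population, so their rates may differ. Historical controls are matched on eligibility only, and no brochure-to-historical ratio is fixed.

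**Working it through.** **Inputs from the SAP (Statistical Power).** Brochures mailed, low-end: 1,990 + 894 + 758 = 3,642. Baseline rate 4.21%, detectable rate 6.55%, provider ICC 0.05, 20 patients per provider, 20% attrition.

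**Assumptions, not in the documents.** Equal numbers of brochure and historical patients overall; site rates 3/4.2/6%; brochure shares as listed below; each provider at one site.

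**1. The plan's own figure.** Design effect = 1 + (20 − 1) × 0.05 = 1.95. Effective number per arm = 3,642 × 0.8 / 1.95 = 1,494. Power for 6.55% against 4.21%, two-sided 5%, is 80.9%, so the stated 80% reproduces. The planned effect on the model's scale is ln[(0.0655/0.9345)/(0.0421/0.9579)] = 0.467.

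**2. How much of a site difference the provider intercept absorbs.**
- An ICC of about 0.05 corresponds to a provider SD of 0.42 on the logit scale: 0.176/(0.176 + 3.29) = 0.051.
- Rates of 3/4.2/6% are logits of −3.476, −3.127 and −2.752, with variance 0.088.
- Without site in the model, the provider variance is about 0.176 + 0.088 = 0.264.
- With 40 patients per provider (20 per group), the sampling variance of a provider's logit is about 1/(40 × 0.0421 × 0.9579) = 0.620.
- The weight on the provider's own data is 0.264/(0.264 + 0.620) = 0.30. About 70% of the between-site signal is not absorbed.

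**3. Approximate shift.** With sites of equal size, pool the rates over sites in each group, take the log odds ratio under no true effect, and multiply by 0.70.

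| Brochure shares by site | Pooled brochure rate | Pooled historical rate | Pooled log OR | × 0.70 |
|---|---|---|---|---|
| 50/50/50% | 4.4% | 4.4% | 0 | 0 |
| 45/50/55% | 4.5% | 4.3% | 0.048 | 0.033 |
| 40/50/60% | 4.6% | 4.2% | 0.095 | 0.067 |

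**4. Simulation.** There were 3,642/20 ≈ 182 providers, taken as 61 per site, with 40 patients each, provider SD 0.42, true odds ratio 1 and 200 replicates. The fitted model was a random-intercept logistic model.

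| Brochure shares | Mean log OR without site | Mean log OR with site | Difference | SD without / with site |
|---|---|---|---|---|
| 50/50/50% | 0.000 | 0.000 | 0.000 | 0.115 / 0.115 |
| 45/50/55% | 0.029 | −0.004 | 0.033 | 0.113 / 0.113 |
| 40/50/60% | 0.071 | 0.006 | 0.065 | 0.105 / 0.106 |

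The simulation agrees with step 3. Reversing the shares to 60/50/40% reverses the sign: −0.079 without site against −0.014 with it. A run with random slopes as well as intercepts, closer to the SAP's model, gave about 0.00 with equal shares, 0.02 to 0.04 with 45/50/55%, and 0.07 with 40/50/60%.

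**5. Scale.** 0.033/0.467 = 7% and 0.067/0.467 = 14% of the planned effect. The estimate's own SD is about 0.11.

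**The case against.** The strongest reply is that sites are never compared with each other. The same providers at the same sites supply both groups under the same eligibility rules, so a stable site difference is common to both. If the brochure-to-historical ratio is equal across sites, omitting site changes nothing, as the first row of each table shows. This stands. The documents report no imbalance, and the same-provider design works against a large one.

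A reader might go further in several ways that the documents do not support.

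- **That site differences do bias the brochure effect.** This requires unequal shares in step with site rates, and neither is given. More extreme assumptions produce larger shifts: shares of 30/50/70% with rates of 2/4.2/8% give a log odds ratio near 0.20. Those shares mean brochure-to-historical ratios from 0.43 to 2.33. Adding that site spread to the provider SD gives a total ICC of 0.138, above even the 0.1 that the SAP uses as a stress case.
- **That randomisation within site obliges adjustment for site.** The protocol says "At each intervention site, individual PCPs will be randomized to the sequence of medication cohorts". This sets the order of the medications, not brochure against control.
- **That the SAP breaks a commitment.** The protocol lists site as a factor to assess. It does not expressly make site a primary-model covariate, and its Provider Effects analysis is exploratory and conditional.
- **That the site variance component rests on three sites.** The SAP does not say that the null model is limited to the intervention sites, and control-site data were also to be collected.
- **That the look-back mismatch distorts the result.** No effect on the estimate has been shown, and nothing indicates that the window differs between groups.

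It is also fair to say that shrinkage applies to providers within a site, which a site term leaves untouched. That limits what the fix achieves, but it is not a reason to leave site out.

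**Conclusion.** The concern holds in a conditional form. The protocol and SAP differ on whether site is among the provider factors, and the primary model as written leaves a route by which stable site differences can reach the brochure coefficient. Under site rates of 3/4.2/6%, the shift is nil with equal brochure shares, about 0.03 to 0.04 on the log odds scale with shares of 45/50/55%, and about 0.07 with 40/50/60%. In the scenarios with unequal shares this is small against the planned 0.467 and less than one SD of the estimate, but it is systematic and could run in either direction. Site rates and shares are assumptions throughout, so the actual size and direction are unknown until counts by site are shown. Adjustment is worth making because it is nearly free, not because a bias has been established. The look-back discrepancy is a separate, minor inconsistency.

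**What to change.** Add site as a fixed effect (three levels, 2 df) to the primary HGLM and to the model for moderation by target medication, and say so in the SAP's covariate paragraph. Report the number of brochure and historical patients and their deprescribing rates at each intervention site, so that a reader can see whether the condition for a shift is met.

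The cost is one CLASS variable in the existing SAS code, one short table and one sentence in the SAP. No new data are needed, and the simulations show no visible loss of precision. The change does not remove site-specific trends over time, or the same shrinkage effect between providers within a site. A sensitivity analysis with provider fixed effects would address the latter.

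As a minor separate correction, state one comorbidity look-back in both documents and apply the same window to both groups.

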Official Title: Engaging Patients to Promote Deprescribing

NCT Number: NCT04294901

Document Date: November 14, 2019

Statistical Power

Based on fiscal year (FY) 2017 data, we estimated that we would mail brochures to at least 1,990 PPI patients, 894 Diabetes-Hypoglycemia patients, and 758 Gabapentin patients during the study. For apriori statistical power analyses, we made the following assumptions based on our pilot data: an overall baseline deprescribing rate of 4.21%, a conservatively high intraclass correlation coefficient (ICC) of 0.05 (for non-independence among patients of the same provider), an average of 20 eligible patients per PCC or WHC provider, and a 20% attrition rate (i.e., patients who receive the intervention brochure but do not attend their clinic visit). With these assumptions, we determined that we would have 80% power (for two-tailed tests at $\alpha=0.05$) to detect deprescribing rates following the intervention as small as 6.55% overall for these low-end estimates of our projected sample. Moreover, even at these low-end estimates of the projected sample size, we determined we would have 80% power to detect an overall deprescribing rate as low as 15% among the combined intervention cohorts even if the ICC was as high as 0.1, the baseline deprescribing rate was as high as 10%, and/or the attrition rate was as high as 40%. Notably, a deprescribing rate of 15% was reasonable to expect given that we found similar or higher rates in our pilot study.

We conducted analyses using SAS.³

Endpoints & Covariates

The primary hypothesis was deprescribing would be greater for Veterans receiving the intervention brochure than for those in the historical control group.

The primary outcome was binary: deprescribing versus not, assessed via pharmacy dispensing data from the VA Corporate Data Warehouse (CDW). More specifically, six months from the index date, an analyst queried the CDW to determine medication outcomes (e.g., complete deprescribing, dose reduction). We selected 6 months because prescriptions are often filled as a 90-day supply and using a shorter observation window might not fully identify that the prescription was not refilled. We removed patients who died within six months from their index data from intervention and historical controls at the analysis stage to avoid misattributing deprescribing to the intervention rather than death.

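### The before-after primary model does not adjust for index dose and days' supply of the target drug, or for HbA1c in the diabetes cohort

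*SAP*

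**What the plan says.** **Covariates.** SAP, Endpoints & Covariates: "patient factors included age, race, sex, and Elixhauser comorbidities in the year prior to the scheduled primary care visit", and "provider characteristics (age, gender, profession) were included as covariates in the model". The protocol (Study Measures) names similar patient and provider factors and adds site. Neither document lists index dose, days' supply or HbA1c. Medication cohort appears only as a moderator, not as a listed main effect.

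**Outcome.** Deprescribing means no refill in the 6 months after the visit or, for oral drugs, a lower TDD. The SAP says "we calculated the total daily dose (TDD) of the target medication as" dose × quantity / days supplied, and "We only compared TDD at 6 months to that at the index visit for oral medications". Insulin is left out of the dose comparison because "insulin dose adjustments are not consistently documented within the electronic health record". The 6-month window was chosen because "prescriptions are often filled as a 90-day supply and using a shorter observation window might not fully identify that the prescription was not refilled". A buffer on days' supply is applied: 10% for oral drugs, 100% for insulin.

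**Eligibility** (Protocol, Medication Groups). All cohorts need 90 days of use. PPI dose is unrestricted, gabapentin must exceed 1800 mg/day, and DM-HR patients must have HbA1c below 7%.

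**Comparison.** Brochure patients are compared with earlier patients of the same providers under the same eligibility rules, seen 12 to 18 months before (Protocol, Study Cohorts). Control sites serve a separate analysis of time trends.

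**Look-back.** The protocol (Study Measures) has "Elixhauser comorbidities in the two years prior to the scheduled primary care visit"; the SAP has one year.

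**The concern.** Two of the omitted variables are part of how the outcome is measured. Index TDD is the reference for every dose reduction. Days' supply governs how easily a run of missed refills fills the window: over about 180 days, a 90-day supply has about 180/90 = 2 refills due and a 30-day supply about 180/30 = 6, so fewer missed refills are needed to count as cessation. HbA1c plausibly marks how over-treated a DM-HR patient is, but that link is weaker and is an inference.

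Providers are randomised to the order of medication cohorts; patients are not randomised to period. If dose mix, fill length or HbA1c drifted among a provider's eligible patients between periods, the model would assign the resulting change in deprescribing to the brochure. The error could go either way, creating an apparent effect or hiding a real one.

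**Working it through.** **1. The plan's own figure.** From SAP, Statistical Power: projected mailings 1,990 + 894 + 758 = 3,642; attrition 20%; ICC 0.05; 20 patients per provider; baseline 4.21%; detectable rate 6.55%. The size of the historical control group is not given, so equal groups are assumed.

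- Attenders: 3,642 × 0.8 = 2,913.6.
- Design effect: 1 + (20 − 1) × 0.05 = 1.95.
- Effective n per group: 2,913.6 / 1.95 = 1,494.
- Power for 4.21% against 6.55%, two-sided 0.05: 0.81. Rate detectable with 80% power: 6.52%.

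The stated 6.55% is reproduced, and the power statement is not at issue. The yardstick is 6.55 − 4.21 = 2.34 points.

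**2. Effect of one omitted factor.** The documents give no distribution of dose, days' supply or HbA1c by period, and no association of any of them with deprescribing. What follows is therefore an illustration. Assumptions: a binary factor present in 50% of controls; an odds ratio (OR) with deprescribing of 1.5, 2 or 3; a prevalence 5, 10 or 20 points higher in the brochure period; no true brochure effect.

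Let p0 and p1 be the rates without and with the factor. Then p1 = OR × p0 / (1 − p0 + OR × p0), with 0.5 × p0 + 0.5 × p1 = 4.21%. The spurious difference is shift × (p1 − p0).

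| OR | p0, p1 (%) | p1 − p0 (points) | shift 5 | shift 10 | shift 20 |
|---|---|---|---|---|---|
| 1.5 | 3.40, 5.02 | 1.62 | 0.08 | 0.16 | 0.32 |
| 2 | 2.86, 5.56 | 2.70 | 0.14 | 0.27 | 0.54 |
| 3 | 2.17, 6.25 | 4.07 | 0.20 | 0.41 | 0.81 |

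As a share of 2.34 points, this is 3% (0.08) to 35% (0.81). With 1,494 effective patients per group, the chance of a significant result favouring the brochure under no effect is 0.032 to 0.184, against a nominal 0.025.

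At the 10% baseline that the SAP also considers, the same grid gives 0.18 to 1.84 points and a chance of 0.036 to 0.365. The detectable difference there, with the same effective n, is 13.29 − 10 = 3.29 points.

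**3. Which variables can be used, and where.**

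- *Index TDD:* available for oral drugs. Its range is open in the PPI cohort (1,990 / 3,642 = 55% of mailings) and bounded below for gabapentin.
- *Days' supply:* usable for oral drugs. For insulin, minimum vials are dispensed regardless of dose, hence the 100% buffer, so the value is unreliable.
- *HbA1c:* an entry criterion in DM-HR only (894 / 3,642 = 25%), and capped below 7% in both periods.

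**4. Room in the model.** At 4.21% and 6.55% with 2,914 patients per group, expected events are 2,914 × (0.0421 + 0.0655) ≈ 310, enough for a few more terms.

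**The case against.** The best defence is that the plan has safeguards and that no imbalance has been shown. Patients are compared within provider under one set of eligibility rules. Entry truncates HbA1c and gabapentin dose equally in both periods. The window and buffers were set with fill length in mind. The covariates come from a stated conceptual model. The control-site analysis found no significant time trend (SAP, Other analytical subsets).

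Much of this stands as a limit on size; it does not close the gap. Same-provider comparison removes differences between providers, not changes in dose or fill mix within one provider's patients. PPI dose stays open. The control-site analysis bears on system-wide change, but it is separate from the primary contrast, comes from sites the protocol itself calls non-equivalent, and cannot show a case-mix shift confined to the intervention sites. A non-significant trend is also not evidence of none.

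A reader might go further and infer that these variables are strongly tied to the outcome, or that half the detectable difference could be artefact. The documents support neither. They contain no association and no shift between periods. An artefact of about half would need something like a 15-point gap in deprescribing between dose groups. At 4.21% overall, that allows at most 4.21 / 15 = 28% of patients in the higher group, with no deprescribing at all in the rest, although non-refill counts at any dose. A reader might also take two years as the correct look-back; nothing in the documents says which was intended.

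**Conclusion.** The omission is real and worth repairing; evidence of actual bias is absent. In the illustration at the 4.21% baseline, small shifts matter little (0.08 to 0.27 points for 5 to 10 point shifts with OR 1.5 to 2). About a third of the detectable difference is reached only with OR 3 and a 20-point shift. These results rest on the assumed prevalence, odds ratios, shifts and equal group sizes; only the trial's data can show where in the range it falls, and in which direction.

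The case is firmest for oral TDD and days' supply, and weakest for HbA1c. Adjustment would not repair another feature of the comparison: patients who later received a brochure are removed from the historical controls (Protocol, Study Cohorts), which selects controls on later status. The look-back conflict is certain, but it is a separate matter of consistency.

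**What to change.** 1. Tabulate pre-brochure TDD (oral drugs), days' supply and DM-HR HbA1c by period and cohort, measured at the same baseline point in both groups.
2. Refit the primary model with these added: medication cohort; TDD standardised within cohort and days' supply for oral drugs; an insulin indicator in place of dose and supply; HbA1c within DM-HR.
3. Report it beside the specified model as a labelled post hoc adjusted analysis. The SAP (Missing Data) already describes results, so it should not replace the primary analysis.
4. Reconcile the comorbidity look-back between protocol and SAP with what was actually run, and apply it identically to both groups.

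**Cost.** A table, one further model fit on variables already used for eligibility or the outcome, and a text correction. The downsides are small: a few extra model terms and the post hoc status of the result.
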